7.1.2.5. Maximum Number of Inhalations Taken In a 24-Hour Period

Summary descriptive statistics of the maximum number of inhalations taken in a 24-hour period will be presented overall and by CE-COPD status and by CE-COPD severity.

Data listings for each parameter of albuterol use will be presented by patient.

7.2. Inhalational Flow Values

7.2.1. Inhalational Flow Values Definitions

Study Day X and Week Y inhalational flow values are defined as follows:

Study Day X Inhalational Flow Values: The inhalational flow values for study day X are computed using the set of inhalations taken by the patient on study day X . Among these inhalations, the inhalation with the highest maximal MIF value is considered the 'Study Day X Inhalation'. The Study Day X MIF, inhalational volume, inhalation duration, and time to MIF values are those of the identified 'Study Day X Inhalation'. If there was no albuterol use on Study Day X , then the closest preceding nonmissing Study Day Inhalation' is used as the 'Study Day X Inhalation' and the inhalational flow values for Study Day X are assigned accordingly.

Week Y Inhalational Flow Values: The inhalational flow values for Week Y are computed using the set of inhalations taken by the patient during a given week on the study. Among these inhalations, the inhalation with the highest MIF value is considered the 'Weekly Y Inhalation'.

The Weekly Y MIF, inhalational volume, inhalation duration, and time to MIF values are those of the identified ‘Weekly Y Inhalation’.

Note, if a patient never used the ABS eMDPI during the study or download of a given ABS eMDPI device was not successful, study day and weekly inhalational flow values will be missing.

7.2.2. Analysis Methods for Inhalational Flow Values

7.2.2.1. Actual and Change from Baseline in Study Day X Inhalational Flow Values Prior to the Peak of a CE-COPD

Among patients who experienced a CE-COPD, summary descriptive statistics of the actual inhalational flow values and change from baseline in daily inhalational flow values for MIF, inhalational volume, inhalation duration, and time to MIF at 1 day (eg, the 24-hour period on the day prior to the date of the CE-COPD symptom peak) and at 3, 5, 7, 10, 14, and 21 days preceding the peak of a CE-COPD, will be presented for all CE-COPDs and by moderate CE-COPDs and severe CE-COPDs.

In this analysis, among patients experiencing more than 1 CE-COPD, the subsequent CE-COPDs will be considered a separate CE-COPD distinct from the first (preceding) CE-COPD, provided the patient exhibited at least 1 day of baseline albuterol use after the first (preceding) CE-COPD’s date of symptom peak and prior to the subsequent CE-COPD’s date of symptom peak. For patients who experience multiple CE-COPDs (eg, 3), for a given number of days preceding a CE-COPD (eg, 7 days), if the (eg, third) CE-COPD overlaps with the time period of the preceding (eg, second) CE-COPD, the CE-COPD (eg, third CE-COPD) should not be included in the analysis.

Summary descriptive statistics of the actual inhalational flow values and change from baseline in daily inhalational flow values for MIF, inhalational volume, inhalation duration, and time to MIF will be presented for overall, by CE-COPD status, by CE-COPD severity (Yes: severe, moderate; No) and for the first occurrence of a single day increase of 20% from baseline use. For patients who experienced a CE-COPD, the single day increase of 20% from baseline use is the single day increase of 20% from baseline use prior to the exacerbation.

In addition, summary descriptive statistics of the maximum change from baseline in daily inhalational flow values for MIF, inhalational volume, inhalation duration, and time to MIF, will be presented overall and by CE-COPD status and by CE-COPD severity (Yes: severe, moderate; No). For patients who experienced a CE-COPD, the maximum change from baseline is the maximum change prior to the exacerbation.

7.2.2.2. Actual and Change from Baseline in Week Y Inhalational Flow Values

Summary descriptive statistics of the actual inhalational flow values and change from baseline in MIF, inhalational volume, inhalation duration, and time to MIF for each study week (1 through 12) will be presented overall, and by CE-COPD status and by CE-COPD severity.

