4.2.3. Inhalational Flow Values

The baseline inspiratory flow values are computed using the set of inhalations taken by the patient during study day 1 through day 7. Among these inhalations, the inhalation with the highest MIF value is considered the ‘baseline inhalation’. The baseline MIF, inhalational volume, inhalation duration, and time to MIF values are those of the identified ‘baseline inhalation’. If no inhalations were taken during study day 1 through study day 7, the ‘baseline inhalation’ is the first available inhalation after study day 7.

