4.2.4. Total Daily Steps

Baseline TDS is the average number of daily steps a patient completes, computed using the daily steps recorded during the first 7 days of study participation (study day 1 through study day 7). The average will be calculated as the sum of the daily TDS divided by the number of days with nonmissing TDS. If no step data are available for study day 1 through study day 7, the ‘baseline TDS’ is the first available TDS after study day 7.

Baseline TDS are computed for those patients in the ankle accelerometry analysis set.

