7.1.1. Albuterol Use Definition

Baseline albuterol use is defined as the mean number of inhalations per day from day 1 to day 7. If no inhalations were taken during study day 1 through study day 7, the ‘baseline inhalation’ is the first available inhalation after study day 7. For analyses relative to baseline albuterol use, patients who had a CE-COPD during study day 1 through study day 7 will be excluded.

Week 1 Patient Albuterol Use: Week 1 patient albuterol use is each patient’s total number of albuterol inhalations taken and the number of days used during the first week (study day 1 through study day 7) of study participation with an indicator of whether or not the most frequent daily usage of albuterol is in 1 of the following 3 categories: (a) 0 to 2 inhalations, (b) 3-6 inhalations and (c) > 6 inhalations. It is presented as WK1:I#iD#dMTN#n, where “i” is the number of albuterol inhalations and “d” is the number of days used in the first 7 days of the study, and “n” is an indicator of whether or not the most frequent daily usage of albuterol falls into one of the 3 categories. If there is a tie in the most frequent daily usage, the category with the highest number of inhalations will be reported. For example, “I28D7MTN2” indicates a total of 28 inhalations were taken, albuterol use was used each of the 7 days and the highest most frequent usage per day falls into category 2 with 3-6 inhalations.

Week 2 Patient Albuterol Use: Week 2 patient albuterol use is each patient’s total number of albuterol inhalations taken and the number of days used during the second week (study day 8 through study day 14) of study participation with an indicator of whether or not the most frequent daily usage of albuterol is in one of the following 3 categories: (a) 0 to 2 inhalations, (b) 3-6 inhalations and (c) > 6 inhalations. It is presented as “WK2:I#iD#dMTN#n”, where “i” is the number of albuterol inhalations and “d” is the number of days used in the second week of study, and “n” is an indicator of whether or not the most frequent daily usage of albuterol is in one of the 3 categories. If there is a tie in the most frequent daily usage, the category with the highest number of inhalations will be reported.

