7.3.2.2. Actual and Change from Baseline in Week Y Total Daily Steps

Summary descriptive statistics of the actual Week Y TDS and change from baseline in TDS for each study week (1 through 12) will be presented overall, and by CE-COPD status and by CE-COPD severity (Yes: severe, moderate; No) using the ankle accelerometry analysis set.

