7.4.2.2. Actual and Change from Baseline in Week Y Sleep Disruption Indices

Summary descriptive statistics of the absolute Week Y nighttime average sleep latency time, longest nighttime wake episode, total time awake at night, and SDI composite score and change from baseline in these 4 SDIs for each study week (1 through 12), will be presented overall, and by CE-COPD status and by CE-COPD severity.

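### SAP change-from-baseline tables include the baseline week itself, and maximum change has no start day or direction, so Week 1 change is an artefact and a fall in MIF or steps can be missed

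*SAP*

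**What the plan says.** Baseline window. For flow (SAP 4.2.3), "The baseline inspiratory flow values are computed using the set of inhalations taken by the patient during study day 1 through day 7". One inhalation then supplies all four parameters: "Among these inhalations, the inhalation with the highest MIF value is considered the" baseline inhalation. For steps (SAP 4.2.4), baseline is an average "computed using the daily steps recorded during the first 7 days of study participation". SAP 4.2.5 averages each sleep parameter over the same days.

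Week 1. SAP 4.5 makes Week 1 Study Days 1 to 7, and SAP 7.1.1 repeats it: "during the first week (study day 1 through study day 7) of study participation". The weekly rules in SAP 7.2.1, 7.3.1 and 7.4.1 match the baseline rules (highest-MIF inhalation, or mean of nonmissing days). The exception is the longest nighttime wake episode, which has a mean at baseline and a weekly maximum.

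Change tables. SAP 7.2.2.2 summarises "change from baseline in MIF, inhalational volume, inhalation duration, and time to MIF for each study week (1 through 12"). SAP 7.3.2.2 asks for "change from baseline in TDS for each study week (1 through 12) will be presented overall", and SAP 7.4.2.2 for "change from baseline in these 4 SDIs for each study week (1 through 12").

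Maximum change. SAP 7.2.2.1 asks for "summary descriptive statistics of the maximum change from baseline in daily inhalational flow values for MIF" and the other flow parameters. SAP 7.3.2.1 and 7.4.2.1 do the same for steps and sleep. For patients with a CE-COPD the search ends at the exacerbation. No start day is given, and nothing says whether the maximum is signed or is the largest change in either direction.

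Exclusion. SAP 4.2.1 and 7.1.1 remove patients with a CE-COPD in Days 1-7 only from analyses relative to baseline albuterol use.

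**The concern.** When the baseline period and the first post-baseline period are the same days summarised by the same rule, the difference carries no information. The Week 1 row will show mean 0 and SD 0 in patients with and without a CE-COPD, including a patient who exacerbates in that week.

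The maximum-change tables have the same overlap in a less visible form. Days 1-7 always contain a day at or above baseline, so a signed maximum starts from a floor of zero. Protocol 2.1.1 uses inspiratory flow as a surrogate for peak expiratory flow, and steps as a correlate of dyspnea on exertion. For MIF and steps deterioration is a fall, and a statistic floored at zero cannot report one.

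**Working it through.** The plan states no figure on this point, so there is none to reproduce. The check applies the SAP's rules literally.

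**1. Week 1 change.**
- Flow: baseline is the highest-MIF inhalation of Days 1-7, and so is Week 1. It is the same inhalation, so all four changes are 0.
- TDS, sleep latency and total time awake: mean of nonmissing days 1-7 minus the same mean = 0. This assumes that imputed Study Day values do not enter the weekly mean, as the reference to nonmissing days suggests.
- Longest wake episode: weekly maximum minus mean, which is at least 0. Example nights of 20, 35, 15, 40, 25, 30, 45 give baseline 210/7 = 30, Week 1 = 45, change +15. The composite inherits this if its baseline is the sum of the component baselines, which the SAP does not spell out.

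**2. Signed maximum over all study days.**
- MIF: on the day of the baseline inhalation, the Study Day inhalation is that same inhalation, so the change is 0 and the maximum is at least 0.
- TDS: the highest of Days 1-7 cannot be below their mean, so the maximum is at least 0.

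**3. Two patients who decline every day for 84 days.**
- MIF = 60 − 0.25 × (day − 1). Baseline 60. Maximum change 0. Change on Day 84 = −0.25 × 83 = −20.75. Week 1 change 0, Week 2 change −1.75.
- TDS = 6000 − 50 × (day − 1). Baseline 5850. Maximum change 6000 − 5850 = +150. Change on Day 84 = 1850 − 5850 = −4000. Week 1 change 0, Week 2 change 5500 − 5850 = −350.
- Searching from Day 8, the maxima become −1.75 and 5650 − 5850 = −200.

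**4. The exception.** With a CE-COPD on Day 4 only Days 1-3 are searched, while baseline uses all seven days.
- MIF of 50, 52, 51, 49, 58, 60, 59: maximum change 52 − 60 = −8.
- TDS of 3000, 2800, 2500, 2000, 4000, 5000, 5200: mean 3500, maximum change 3000 − 3500 = −500.
- At the SAP 2.3 rates, Days 1-7 would hold between 360 × 1.05 × 7/365.25 = 7.2 and 400 × 1.14 × 7/365.25 = 8.7 events.

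**5. Size with day-to-day noise.** Assumptions: symptom peak on Day 42 (41 days searched) and a sustained fall from Day 8.
- MIF (mean set to 100, 4 inhalations a day), 20% fall: maximum change is exactly 0 in essentially 100% of patients at within-patient CV 5% or 10%, and in 94% at CV 20%. From Day 8 the mean maximum is about −19 at CV 10%. For a 10% fall the share at exactly 0 is nearly 100%, 86% and about 60% at CV 5%, 10% and 20%.
- TDS (mean 5804, from the cohort cited in protocol 3.3), 20% fall, true mean change about −0.20 × 5804 = −1161:

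| Day-to-day CV | Mean maximum as written | Mean maximum from Day 8 | Maximum from Day 8 still positive |
|---|---|---|---|
| 20% | about +1650 | about +780 | 90% |
| 30% | about +2610 | about +1760 | 97% |
| 40% | about +3620 | about +2720 | 99% |

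Moving the start to Day 8 repairs MIF. For steps it removes the floor, but a signed maximum of noisy data still shows an increase.

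**The case against.** The best defence is that these are descriptive tables in an exploratory study, with no test or decision attached, and that a Week 1 row of 0 with SD 0 beside actual values is recognisable as the baseline row. That bears on severity, but a change row that cannot vary should still not be produced.

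A second defence is that maximum change may mean the largest change in either direction with its sign kept. The two patients in step 3 would then show −20.75 and −4000, and the floor disappears. The SAP does not choose, so this does not rescue the text. It makes direction part of the defect.

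A reader might infer three stronger things that the documents do not support:
- That Week 1 change is zero for every patient and every measure. It is missing where there are no Day 1-7 data, and two of the four sleep measures can be positive.
- That maximum change can never be negative. Step 4 gives the exception for MIF and TDS. Under the fallback baseline, volume, duration or time to MIF can also have a negative maximum, though this was rare in simulation (under 1%).
- That a decline before an exacerbation is hidden from the report. SAP 7.2.2.1, 7.3.2.1 and 7.4.2.1 also give change at 1, 3, 5, 7, 10, 14 and 21 days before the peak, and the weekly tables cover Weeks 2-12. The adjacent-week comparison in SAP 7.5.2.1 does not use this baseline at all. In the 20% MIF fall at CV 10%, change on the day before the peak averages −32.

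For sleep latency and time awake, worsening is an increase, so a floor at zero does not suppress it. For time to MIF too, worsening need not be a decrease.

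**Conclusion.** The point stands within limits. The Week 1 result follows from the SAP's definitions and needs no numerical assumption beyond the handling of imputed days: 0 for seven measures, and zero or positive for two, in patients with Day 1-7 data. The maximum-change result holds if the maximum is signed and taken over all study days, which is the literal reading but not a stated one. On that reading it cannot be negative for MIF or TDS, apart from patients whose CE-COPD falls in Days 1-7 (about 7 to 9 events expected). The simulated percentages rest on assumed CVs, the assumed timing of the fall and, for MIF, an assumed 4 inhalations a day. They show scale and are not predictions.

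The harm is limited to the Week 1 change rows and the maximum-change tables. It is worth correcting because those tables would otherwise report no change, or an increase, in patients whose flow or activity has fallen.

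**What to change.** - In SAP 7.2.2.2, 7.3.2.2 and 7.4.2.2, report change from baseline for Weeks 2 to 12 only, and keep the actual values for Week 1.
- In SAP 7.2.2.1, 7.3.2.1 and 7.4.2.1, search for maximum change from Study Day 8 onward. Replace the single maximum with the largest decrease and the largest increase, reported separately, with the largest decrease as the relevant one for MIF and TDS. The start day alone is not enough, as the step table in the working shows.
- Extend the Day 1-7 CE-COPD exclusion in SAP 4.2.1 to the flow, TDS and sleep change analyses.

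The cost is SAP wording and small edits to the derivation programs, with no new data. Patients whose CE-COPD peaks by Day 8 leave the maximum-change tables, and their number should be shown in a footnote. Extremes in either direction also grow with the number of days searched, so that number should be reported beside them.

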7.3. Accelerometry: Total Daily Steps

7.3.1. Total Daily Steps Definition

Study Day X and Week Y TDS are defined as follows:

Study Day X TDS: The TDS for study day X are the TDS recorded by accelerometry on study day X . If TDS are missing on Study Day X , then the average TDS of the 7 days preceding study day X is computed and assigned to Study Day X .

Week Y TDS: The TDS for Week Y are computed using the set of TDS taken by the patient during a given week on study. The average will be calculated as the sum of the daily TDS divided by the number of days with nonmissing TDS.

The TDS are computed for those patients in the ankle accelerometry analysis set.

7.3.2. Analysis Methods for Total Daily Steps

7.3.2.1. Actual and Change from Baseline in Study Day X Total Daily Steps Prior to the Peak of a CE-COPD

Among patients in the ankle accelerometry cohort who experienced a CE-COPD, summary descriptive statistics of the actual TDS and change from baseline in TDS 1 day (eg, the 24-hour period on the day prior to the date of the CE-COPD symptom peak) and at 3, 5, 7, 10, 14, and 21 days preceding the peak of a CE-COPD, will be presented for all CE-COPDs and by moderate CE-COPDs and severe CE-COPDs.

In this analysis, among patients experiencing more than 1 CE-COPD, the subsequent CE-COPDs will be considered a separate CE-COPD distinct from the first (preceding) CE-COPD provided the patient exhibited at least 1 day of baseline albuterol use after the first (preceding) CE-COPD's date of symptom peak and prior to the subsequent CE-COPD's date of symptom peak. For patients who experience multiple CE-COPDs (eg, 3), for a given number of days preceding a CE-COPD (eg, 7 days), if the (eg, third) CE-COPD overlaps with the time period of the preceding (eg, second) CE-COPD, the CE-COPD (eg, third CE-COPD) will not be included in the analysis.

Among patients in the ankle accelerometry cohort, summary descriptive statistics of the actual TDS and change from baseline in TDS, will be presented for overall, by CE-COPD status, by CE-COPD severity (Yes: severe, moderate; No) and for the first occurrence of a single day increase of 20% from baseline use. For patients who experienced a CE-COPD, the single day increase of 20% from baseline use is defined as the single day increase of 20% from baseline use prior to the exacerbation.

In addition, summary descriptive statistics of the maximum change from baseline in TDS will be presented overall and by CE-COPD status and by CE-COPD severity. For patients who experienced a CE-COPD, the maximum change from baseline in TDS is the maximum change from baseline in TDS during the days prior to the exacerbation.

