(Moy et al 2013), physical activity was directly assessed using the StepWatch Activity Monitor, an ankle-worn accelerometer that measures daily step count. Also assessed were exercise capacity, using the 6-minute walk test (6MWT), and patient-reported physical activity using the St. George's Respiratory Questionnaire Activity Score (SGRQ-AS). Adverse events and COPD-related hospitalizations were assessed and validated prospectively over a median of 16 months.

Mean daily step count was 5804 ± 3141 steps. Over 209 person-years of observation, there were 263 adverse events (incidence rate 1.36 ± 1.6 per person-year) and 116 COPD-related hospitalizations (incidence rate 0.56 ± 1.09 per person-year). Adjusting for FEV₁ percent predicted and prednisone use for adverse events in the previous year, for each 1000 fewer steps per day walked at baseline, there was an increased rate of adverse events (rate ratio 1.07; 95% CI=1.003 to 1.15) and COPD-related hospitalizations (rate ratio 1.24; 95% CI=1.08 to 1.42). There was a significant linear trend in decreasing daily step count by quartiles and increasing rate ratios for adverse events ($p=0.008$) and COPD-related hospitalizations ($p=0.003$). Each 30-m decrease in 6MWT distance was associated with an increased rate ratio of 1.07 (95% CI=1.01 to 1.14) for adverse events and 1.18 (95% CI=1.07 to 1.30) for COPD-related hospitalizations. Worsening of SGRQ-AS by 4 points was associated with an increased rate ratio of 1.05 (95% CI=1.01 to 1.09) for adverse events and 1.10 (95% CI=1.02 to 1.17) for COPD-related hospitalizations. Lower daily step count, lower 6MWT distance, and worse SGRQ-AS predict future adverse events and COPD-related hospitalizations, independent of pulmonary function and previous adverse event history. These results support the importance of assessing physical activity in patients with COPD and provide the rationale to promote physical activity as part of exacerbation-prevention strategies.

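### The maximum change from baseline in steps and flow has no stated direction, and it is searched over fewer days in patients with CE-COPD than in those without

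*SAP*

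**What the plan says.** SAP 7.3.2.1 adds to the step-count tables one extreme-value summary per patient: "summary descriptive statistics of the maximum change from baseline in TDS will be presented overall", and also by CE-COPD status and severity. For patients with an event, "the maximum change from baseline in TDS is the maximum change from baseline in TDS during the days prior to the exacerbation". No matching limit is set for patients without an event.

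SAP 7.2.2.1 repeats the pattern for flow: "summary descriptive statistics of the maximum change from baseline in daily inhalational flow values for MIF, inhalational volume, inhalation duration, and time to MIF", again by status and severity and again limited to the time before the exacerbation in patients who had one. SAP 7.4.2.1 does likewise for three sleep measures.

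None of these sections says whether the maximum is the largest signed value, the largest absolute change or the largest worsening.

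The baselines differ. SAP 4.2.4: "Baseline TDS is the average number of daily steps a patient completes, computed using the daily steps recorded during the first 7 days". For flow, SAP 4.2.3 takes a best value: "Among these inhalations, the inhalation with the highest MIF value is considered the" baseline inhalation.

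On direction, Protocol 3.3 reports from a cited cohort that "for each 1000 fewer steps per day walked at baseline, there was an increased rate of adverse events", and concludes: "Lower daily step count, lower 6MWT distance, and worse SGRQ-AS predict future adverse events and COPD-related hospitalizations". Protocol 2.1.1 describes TDS as a correlate of exertional dyspnea. It uses inspiratory flow as a stand-in for peak expiratory flow, whose deterioration it lists among the features studied in relation to later CE-COPD.

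**The concern.** There are two separate problems.

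**Direction.** The largest value of (daily value minus baseline) is the largest rise, so for steps it picks the patient's most active day. The protocol's reasons for measuring steps and flow point to a fall in TDS and in MIF. A statistic that picks the upper extreme can look the same whether or not a fall occurred. If another programmer took the largest absolute change, the table would differ and the SAP would not settle which was right.

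**Window.** For a given patient, the maximum over some of the days can never exceed the maximum over all of them. Cutting the search at the exacerbation in one group only therefore pushes that group's maximum down. The comparison by CE-COPD status then mixes any true difference with the number of days searched.

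At stake is whether the table can be read as evidence on what happens to activity and flow before an exacerbation.

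**Working it through.** The plan states no figure that depends on this definition, so there is none to reproduce. The calculations below illustrate size only.

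**1. Which extreme does the wording select?** SAP 7.5.2.1 asks for a *minimal* daily time to MIF when it wants a lower extreme. That supports reading *maximum* algebraically, as the largest signed value, but does not prove it.

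**2. Effect of window length alone.** For n independent standard normal days the expected maximum is E(n) = ∫ x · n · φ(x) · Φ(x)^(n−1) dx.
- E(84) = 2.445 and E(42) = 2.181, so the difference is 2.445 − 2.181 = 0.264 SD.
- For the largest absolute value the figures are 2.69 and 2.45 SD, a difference of 0.24 SD.

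The 42-day window is an assumption (half of follow-up).

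**3. Effect of window length with an estimated baseline.** This is a simulation of 20,000 patients per setting.
- From the SAP: baseline is the mean of days 1 to 7, and follow-up is 84 days.
- Assumed, because the documents do not give it: independent normal days; within-patient daily SD of 1000 or 2000 steps; change searched from day 8; symptom peak uniform on days 15 to 84. Protocol 3.3 gives a mean of 5804 and an SD of 3141 steps in the cited cohort, but no within-patient daily SD.
- Days searched: 84 − 7 = 77 without an event; on average 49.5 − 8 = 41.5 with one.

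Mean of the summary in steps, **no true fall** (differences taken before rounding):

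| Daily SD | Summary | No CE-COPD | CE-COPD | Difference |
|---|---|---|---|---|
| 1000 | largest rise | 2414 | 2097 | −316 |
| 1000 | largest absolute change | 2802 | 2514 | −288 |
| 1000 | largest decrease | −2414 | −2103 | +311 |
| 2000 | largest rise | 4833 | 4202 | −631 |
| 2000 | largest absolute change | 5618 | 5017 | −601 |
| 2000 | largest decrease | −4839 | −4190 | +650 |

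Each gap is about 0.3 SD (for example 316/1000 and 631/2000, both 0.32).

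**4. Sensitivity to a true fall, with equal windows.** The peak is on day 84, with a fall of 1000 or 2000 steps on the 7 days before it.

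| Daily SD | Fall | Largest rise: without → with fall | Shift | Largest decrease: without → with fall | Shift |
|---|---|---|---|---|---|
| 1000 | 1000 | 2406 → 2372 | 34 | −2404 → −2663 | 259 |
| 1000 | 2000 | 2406 → 2371 | 35 | −2412 → −3388 | 976 |
| 2000 | 1000 | 4819 → 4767 | 52 | −4819 → −4980 | 161 |
| 2000 | 2000 | 4829 → 4761 | 68 | −4820 → −5346 | 526 |

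The largest rise moves by 34 to 68 steps and the largest decrease by 161 to 976.

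**5. Changing the direction without the window.** With SD 2000, a true fall of 1000 steps and the unequal windows of step 3, the mean largest decrease is −4839 without CE-COPD and −4532 with it. The group that really fell appears to have fallen 307 steps less. The two corrections therefore have to be made together.

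**6. Flow.** These sizes do not carry over to flow, because its baseline is already the best of seven days. The direction of the window effect does carry over, since it comes only from searching fewer days.

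**The case against.** The strongest reply is that this is one additional descriptive table in an exploratory study, with no test attached, and that falls are well covered elsewhere. SAP 7.3.2.1 and 7.2.2.1 also report signed change from baseline at 1, 3, 5, 7, 10, 14 and 21 days before the symptom peak. SAP 7.3.2.2 and 7.2.2.2 report signed change for each of weeks 1 to 12. This stands. A reader might infer that a fall in steps or flow would go unreported; it would not, and only this summary is affected. TDS is also collected only in a planned subset of 100 patients.

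Second, *maximum change* is undefined rather than defined as a rise. The same phrase covers steps, flow and sleep, which fits an absolute-change reading. This stands in part: the signed reading is the literal one, but it should not be stated as the SAP's definition. The window problem is the same under either reading.

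Third, the step evidence in Protocol 3.3 relates a lower level at baseline to later events, which is a comparison between patients. One might read it as showing that a fall within a patient precedes an exacerbation, but it does not say that. The within-patient fall is an inference from the dyspnea rationale and from the interest in changes stated at the end of Protocol 3.3.

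Fourth, a fall as the adverse direction is supported for MIF, through the peak-flow rationale. The documents give no adverse direction for inhalational volume, inhalation duration or time to MIF.

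**Conclusion.** The point holds as a minor specification defect with two parts. The direction of the summary is missing, and its literal reading is nearly blind to the fall in TDS and MIF that the rationale makes interesting. The unequal window biases the comparison by CE-COPD status under any reading, by about 0.3 SD in the step illustration.

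A reader might infer that the unequal window could reverse the expected pattern. Under the signed maximum it does not: it lowers the CE-COPD group and so mimics reduced activity or flow. With a largest-decrease summary it acts the other way and would mask a true fall.

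The sizes rest on independent normal days, an assumed within-patient SD and assumed event times. Correlation between days would change them. That a shorter search lowers the expected maximum does not depend on those choices. The consequence is limited to this summary and its sleep counterpart in SAP 7.4.2.1; no test, sample-size figure or signed summary is affected.

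**What to change.** In SAP 7.3.2.1 and 7.2.2.1, define the summary as the largest decrease from baseline for TDS and MIF. State a direction, with a reason, for inhalational volume, inhalation duration and time to MIF. Keep the maximum for the sleep measures in SAP 7.4.2.1, where more time awake is the unfavourable direction.

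Compute every such extreme, including the sleep measures, over windows of equal length in patients with and without CE-COPD. Options are one value per study week, or a fixed number of days before the symptom peak set against a window of the same length and study time in patients without an event.

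The cost is SAP wording and programming. No new data are needed.
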